2.2 RISK/BENEFIT ASSESSMENT

2.2.1 KNOWN POTENTIAL RISKS

AVH symptomatology

Immediate risk

- Auditory verbal hallucinations can have different qualities such as being commenting, commanding, and/or threatening (e.g. harming oneself and others). These qualities can change over time and are thought to be related to factors such as stress (Upthegrove et al., 2016). AVHs during a phase of florid psychosis can have a more threatening character which in turn can lead to more stress and more psychotic symptoms. Therefore, a close monitoring of the patients' hallucinations, well-being, and the content of the AVH is important. All study personnel are trained to detect signs of stress in patients and worsening of psychotic symptoms. Additionally, the Believes About Voices Questionnaire (BAVQ-R) will be given to patients at every visit to assess the content, severity, and distress associated with AVH. Patients will be asked to report about their AVH's content and will be encouraged by the study coordinator to talk about changes in their mood and AVH content.
- In case a patient shows worsening of psychotic symptoms or, in the worst case, gets suicidal or homicidal within the three days of the study, participation is terminated and appropriate actions are initiated in accordance with the ward such as the application of antipsychotic medication given by the patient's treating clinician as per standard treatment guidelines and based on their best judgment. For this reason, the study staff will be in constant contact with the unit staff and the treating physician of the patient to work together with the best clinical interest for the patients' health.

Long-range risks

- There are no known long-range risks

Blood sample

Immediate risks

- We will obtain a blood sample to assess the serum concentration of the antipsychotic at the moment of hospitalization by adding an extra tube to the 2 that are routinely obtained via simple venipuncture as part of routine care in the emergency room. No phlebotomy will be performed at this point with a research indication if there is no clinical indication as per routine care. The additional blood sample will be collected in a third tube (approximately 2-3 mLs) from the same venipuncture for all patients that are hospitalized and potentially eligible to participate in the study. Therefore, the additional tube that is needed for the study does not constitute an additional risk.

Long-range risks

- There are no known long-range risks.

MRI

Immediate risks

- The risks of fMRI scanning are minimal. There is no ionizing radiation involved in MRI, and there have been no documented significant side effects of the magnetic fields and radio waves used on the human body to date.
- People have been harmed in MRI machines when they did not remove metal objects from their clothes or when others left metal objects in the room. All necessary precautions will be taken to prevent inadvertent presence of metal objects in the MRI room.
- Some subjects, even those without known history of claustrophobia may experience discomfort or even panic attacks in the enclosed setting of the magnet. All efforts will be taken to first calm subjects down and next to decide together with the participant whether or not to continue study participation. All subjects are informed that they can discontinue the procedure at any time, and receive instructions before scanning about communicating with the scanning system operators, which can be done either by a squeeze bulb kept in the subject's hand, or by voice through a microphone mounted inside the bore of the magnet, if they feel uncomfortable. Although, these scans are being done for research purposes, the images from the MRI will be reviewed by a physician who normally reads such images (such as a neuroradiologist). As a result, the subject will be informed of any unexpected findings. If our research yields any information that can be relevant in the subject's clinical management, we will notify them.

The occurrence of the MRI procedure and the subject's study participation may be documented in their medical record.

Long-range risks

- However, because the effects of strong magnetic fields on a fetus are not well documented at this time, pregnant women will be excluded from the study. Pregnancy is assessed with a pregnancy test prior to the two MRI measurements. People have been harmed in MRI machines when they did not remove metal objects from their clothes or when others left metal objects in the room.
- All necessary precautions will be taken to prevent inadvertent presence of metal objects in the MRI room. Some subjects, even those without known history of claustrophobia may experience discomfort or even panic attacks in the enclosed setting of the magnet. All efforts will be taken to first calm subjects down and next to decide together with the participant whether or not to continue study participation. An additional discomfort can be caused by the loud noise generated

by the rapidly changing magnetic field. It is standard to use earplugs or protective headphones to avoid discomfort and sensorineural hearing loss.

rTMS

Immediate risks

- TMS is a non-invasive treatment that is generally safe and well-tolerated. If local scalp pain or face muscle pain occurs, adjustment of the coil usually alleviates the pain. The most significant safety concern is seizure; however, as can be seen from Table 3, 1Hz rTMS for 1800 seconds is considered safe(Rossi et al., 2009). As a safety precaution, however, we will exclude patients with seizure disorders from this study. There are no additional significant risks due to study procedures.

Long-range risks

- The most common side effect is headache or pain, which is transient and responds well to combination of acetaminophen and ibuprofen (we will administer if patients require so). There are no known mechanisms through which the induced magnetic field produced during TMS stimulation could generate biological adverse effects in the absence of extraneous implanted metal in the skull or brain. That is the reason we will exclude all patients with metal implants (they would not be eligible because of the MRI component either).

Maximum established safe train of durations with rTMS

Frequency	Intensity (% of MT)				
	90%	100%	110%	120%	130%
1 Hz	> 1800.00 s	> 1800.00s	< 1800.00 s	> 360.00 s	> 50.00 s
5 Hz	> 10.00 s	> 10.00 s	> 10.00 s	> 10.00 s	> 10.00 s
10 Hz	> 5.00 s	> 5.00 s	> 5.00 s	4.20 s	2.90 s
20 Hz	2.05 s	2.05 s	1.60 s	1.00 s	0.55 s
25 Hz	1.28 s	1.28 s	0.84 s	0.40 s	0.24 s

Note.: s, seconds; MT, motor threshold; '>', maximum tested durations.

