6.4 STUDY INTERVENTION COMPLIANCE

Compliance to study intervention is firstly confirmed by the patient signing the informed consent form. If patients do not want to continue treatment and finish all 4 rTMS sessions together with pre- and post-imaging and interviews, they will be excluded from the study which will be mentioned in the case report form. The data collected up to this point will not be included in the analysis because the primary outcome is the outcome measure of the HCS for which all three measures (baseline, after the last rTMS session, post-MRI) are necessary to reasonably estimate the symptom trajectory.

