7 STUDY INTERVENTION DISCONTINUATION AND PARTICIPANT DISCONTINUATION/WITHDRAWAL

7.1 DISCONTINUATION OF STUDY INTERVENTION

Discontinuation from rTMS does not mean discontinuation from the study, and remaining study procedures should be completed as indicated by the study protocol. If a clinically significant finding is identified (including, but not limited to changes from baseline indicated by a score of 3 (“mild”) or less for all four items of the positive symptom BPRS-subscale (Robinson et al., 2015)) after enrollment, the investigator or qualified designee will determine if any change in participant management is needed. Any new clinically relevant finding will be reported as an adverse event (AE).

The data to be collected at the time of study intervention discontinuation will include the following:

- Reason for discontinuation
- Positive symptoms BPRS-subscale rating
- BAVQ-R rating
- MRI measurements

The specimens of individuals for whom an extra vial of blood was extracted for potential serum antipsychotic concentration analysis that later do not consent to participate in the study will be destroyed immediately without being processed.

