7.2 PARTICIPANT DISCONTINUATION/WITHDRAWAL FROM THE STUDY

Participants are free to withdraw from participation in the study at any time upon request. Nevertheless, subjects may be prematurely terminated from the study if the investigators assess that the subject's clinical condition requires treatment(s) not available within the study context.

An investigator may discontinue or withdraw a participant from the study for the following reasons:

- Pregnancy as assessed with a pregnancy test before the two MRI measurements
- Significant study intervention non-compliance
- If any clinical adverse event (AE), laboratory abnormality, or other medical condition or situation occurs such that continued participation in the study would not be in the best interest of the participant
- Disease progression which requires discontinuation of the study intervention
- If the participant meets an exclusion criterion (either newly developed or not previously recognized) that precludes further study participation
- Participant unable to receive rTMS 4 times for one day
- If patients experience side effects that they are not willing to endure (such as headaches for example)
- Any medical condition which requires treatment with a medication with psychotropic effects
- Significant risk of suicidal or homicidal behavior (including aggressive behavior towards staff, others or themselves)
- MR Imaging contraindications
- Moving of patient or end of status as an in-patient at the Zucker Hillside Hospital

Duration of non-compliance will be determined by the trained study coordinator. Patients will be monitored closely by the study coordinator and all trained staff of the study. Changes i.e. in medication will be assessed before every visit/intervention.

If the patient had to have antipsychotics given because of an emergency or worsening of psychotic symptoms, then they are terminated from the study. However, we will also communicate on the ward that the patient's well-being is of main concern. Thus, should a patients' condition worsen and antipsychotics are thought to be the best help than medication should always be given regardless of the patient being enrolled in the study.

The reason for participant discontinuation or withdrawal from the study will be recorded on the Case Report Form (CRF). Subjects who sign the informed consent form and are randomized but do not

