9.3 POPULATIONS FOR ANALYSES

Data of all patients who attended pre-MRI and interview, 4 sessions of rTMS, and post-MRI and interview will be included in the analysis.

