9.4 STATISTICAL ANALYSES

9.4.1 GENERAL APPROACH

Descriptive statistics will include all patients who completed the study. Patient groups (stratified according to either their sham or real rTMS treatment) will be compared concerning age, sex, socio economic status, general psychopathology (CGI, GAF), severity of AVH (BPRS-subscale, BAVQ-R), and cognitive outcome (rBANS). In particular, mean (standard deviation) together with the range (min, max) will be assessed for the two groups.

Inferential statistics: the p-value will be set to 5% and therefore every value below this threshold is considered significant. Effect sizes will be calculated as well to evaluate if we are dealing with a clinically important effect. Covariates will be included in the analyses such as age and sex.

General assumptions of heterogeneity and normality will be assessed before any subsequent analysis. Based on this either parametric or non-parametric tests will be chosen.

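### Patients withdrawn for worsening have no required exit HCS and are then left out and replaced, or scored at the baseline 10, so their outcomes do not reach the primary comparison

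*Combined protocol and SAP*

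**What the plan says.** The HCS is the primary outcome. Section 1.1 schedules it at baseline, after the last rTMS session and after the post-treatment MRI. Section 3 fixes the baseline at 10 for every patient, and later scores run from 0 to 20.

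**Who leaves.** For a patient who shows "worsening of psychotic symptoms or, in the worst case, gets suicidal or homicidal within the three days of the study, participation is terminated" (2.2.1). Section 7.2 also terminates anyone given antipsychotics for an emergency or for worsening, and 8.3.5 withdraws patients with a serious or intolerable adverse event.

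**What is collected.** Section 7.1 states: "The data to be collected at the time of study intervention discontinuation will include the following". It then names the reason, the BPRS positive-symptom subscale, the BAVQ-R and the MRI. The HCS is not on the list. For withdrawal from the study, 7.2 asks only that the reason go on the case report form. Patients who merely stop stimulation are treated differently: "Discontinuation from rTMS does not mean discontinuation from the study, and remaining study procedures should be completed" (7.1), so their final HCS is still due.

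**What is analysed.** Section 9.3: "Data of all patients who attended pre-MRI and interview, 4 sessions of rTMS, and post-MRI and interview will be included in the analysis". Section 9.4.1: "Descriptive statistics will include all patients who completed the study". Section 6.4 says of patients who do not wish to continue that "The data collected up to this point will not be included in the analysis", on the ground that for the HCS "all three measures (baseline, after the last rTMS session, post-MRI) are necessary". Section 7.2 has treated patients who leave replaced, and permits replacement of those randomised but untreated. Section 8.1 instead analyses drop-outs and premature exits, essentially those who leave before completing four sessions, by last observation carried forward.

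**The concern.** Termination for worsening is related to the outcome the trial measures. If the outcome is not collected at that point and the patient is then dropped and replaced by someone who completes, the analysed groups are no longer the randomised groups. The other rule in the plan, carry-forward, does not repair this: a patient who exits before the last session has no scheduled HCS except the anchor, so a worsened patient is recorded as unchanged. Under either rule an early exit for worsening can never contribute a score above 10.

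The trial tests superiority of real over sham rTMS at the 5% level, and section 9.2 says a detected effect may be the basis for a larger study. A distorted contrast would carry into that decision.

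**Working it through.** **1. The plan's own figure.** Section 9.2 gives 20 per arm for d = 0.9, 80% power and alpha 5%. The two-sided normal approximation is 2 × (1.960 + 0.842)² / 0.9² = 19.4, so 20 per arm, which reproduces the stated 40. (The exact t-test needs 20.39; power at 20 is 79.2%.) There is no allowance for withdrawals, so the plan relies on replacement to reach 40.

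**2. What happens to a patient withdrawn for worsening.**

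| Time of exit | HCS available | 9.3 | 8.1 |
|---|---|---|---|
| Before the last session | Anchor of 10 only | Excluded | Scored 10 |
| After session 4, before the final visit | HCS taken after the last session | Excluded, score discarded | Definitions do not cover this patient |
| Stops rTMS early but stays to the end | Final HCS under 7.1 | Excluded | Carry-forward stated |

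**3. Shift per patient.** Let one patient of 20 in an arm have a true HCS of x, and let the others have mean m. Excluding the patient moves that arm's mean by (x − m)/20. Carrying forward 10 moves it by (x − 10)/20.

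**4. Illustration in d.** The documents give no SD, arm means or withdrawal rate, so these are assumptions: 20 per arm, SD 3, sham mean 9.0, and d = 0.90 among the other patients, so real mean = 9.0 − 0.90 × 3 = 6.3. One real-arm patient worsens to 15.

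- Analysed: real mean = (19 × 6.3 + 15)/20 = 6.735 and the difference is 2.265. Expected real-arm variance = [18 × 9 + (19/20) × (8.7² + 9/19)]/19 = 12.33. Pooled SD = √((9 + 12.33)/2) = 3.27. d = 0.69.
- Carried forward at 10: real mean = 129.7/20 = 6.485 and the difference is 2.515. Variance = [162 + 0.95 × (3.7² + 9/19)]/19 = 9.23, pooled SD 3.02. d = 0.83.
- Excluded and replaced: d = 0.90, by construction.

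At SD 5 the first two values are 0.76 and 0.84. For x from 12 to 18, the analysed d runs from 0.78 to 0.61 at SD 3. The same patient placed in the sham arm gives 0.96, so there the plan understates the effect.

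**5. Withdrawal by a threshold in both arms.** Same means, SD 3, everyone above HCS 12 withdrawn; normal scores, not bounded at 0 or 20.

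- Sham: z = 1, 15.9% withdrawn (3.2 of 20). Completer mean = 9 − 3 × 0.2420/0.8413 = 8.14.
- Real: z = 1.9, 2.9% withdrawn (0.6 of 20). Completer mean = 6.3 − 3 × 0.0656/0.9713 = 6.10.
- Completers: 8.14 − 6.10 = 2.04, against a true 2.70.
- Carry-forward at 10: sham 0.841 × 8.14 + 0.159 × 10 = 8.43; real 0.971 × 6.10 + 0.029 × 10 = 6.21; difference 2.22.

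With a cut-off of 14, the completer difference is 2.43. If both arms have the same distribution, there is no bias.

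**The case against.** The strongest reply is that the size is unknown and the direction is not necessarily favourable to rTMS. That stands. In step 4 the 0.90 holds only because it is defined without the worsened patient, and under the same normal model a real-arm score above 15 is rare: 0.04 of 20 patients at SD 3 and 0.36 at SD 5. SD 5 also fits the 0–20 scale poorly, with about 18% of real-arm scores below zero. Step 5, where one rule applies to both arms, biases against rTMS. Participation lasts at most four days, and the trial is a declared pilot.

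Some stronger readings are tempting, and the documents do not support them:

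- That every withdrawal hides a worsened HCS. The rule in 2.2.1 concerns psychotic symptoms generally, the HCS rates hallucinations only, and a serious adverse event such as a seizure need not raise it.
- That 6.4 and 9.4.3 also exclude these patients from the primary analysis. Section 6.4 speaks of patients who do not want to continue, and 9.4.3 covers secondary endpoints. For patients terminated by the investigator, exclusion rests on 9.3.
- That the worsening disappears from the trial. Section 8.3.4 records deterioration as an adverse event, 2.2.1 gives the BAVQ-R at every visit, and 7.1 collects the BPRS subscale and BAVQ-R when stimulation stops. These allow a supportive analysis but do not supply an HCS value.
- That 7.2 conflicts with the safety sections because it makes optional some withdrawals that they require. Withdrawing satisfies every section, so this is not a defect.

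None of this supplies the missing HCS or reconciles 8.1 with 9.3.

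**Conclusion.** The point holds. HCS outcomes of patients withdrawn for worsening are missing from the primary comparison under 9.3, or scored as unchanged under 8.1 if they leave before the fourth session. A valid score taken after the last session is discarded if the patient then leaves. More worsening on real rTMS flatters it, more on sham understates its effect, and equal distributions give no bias.

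A reader might infer that the plan is tilted towards a positive result, or that d is inflated from 0.69 to 0.90. Neither follows. The figures illustrate how far one or a few patients can move a 20-per-arm comparison under assumed means, SD and exit scores; they do not estimate the bias in this trial. The change should be made before exit scores are lost, since an HCS not taken at withdrawal cannot be recovered.

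**What to change.** 1. Add the HCS to the list in 7.1. Have the blinded rater request it at any withdrawal under 7.2 where the patient agrees, before antipsychotics where that is safe, and never delaying treatment. The safety rules in 2.2.1 and 8.3.5 stay as they are.
2. Amend 6.4, 8.1 and 9.3 so that the primary analysis includes all randomised patients with any post-baseline HCS, in their assigned group. Count the exit HCS as a post-baseline value and state in advance which time it belongs to. Do not carry the anchor of 10 forward. Let replacements add to withdrawn patients, not substitute for them.
3. In 9.4.2 use a method that keeps partial records, for example a mixed model of the two post-baseline HCS times. Report withdrawals and reasons by arm, and run a sensitivity analysis with missing HCS set at values from 10 to 20.

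The cost is wording in these sections and one short rating per withdrawn patient. A few HCS values will be off schedule, some after partial treatment, and the analysed N may slightly exceed 40. In the step 4 illustration, keeping the worsened patient and adding a replacement (21 versus 20) gives d = 0.70, close to the 0.69 without a replacement.

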This heterogeneity of results may be due to influencing factors such as rTMS protocols, parameters, and target regions. Nevertheless, a number of meta-analyses (Aleman, Sommer, & Kahn, 2007; Demeulemeester et al., 2012; Freitas, Fregni, & Pascual-Leone, 2009; C. W. Slotema, Blom, van Lutterveld, Hoek, & Sommer, 2014; C. W. Slotema, Dirk Blom, Hoek, & Sommer, 2010; Tranulis, Sepehry, Galinowski, & Stip, 2008) found significant effect sizes ranging from 0.42 to 1.04 for LF rTMS over the left TPJ. This indicates a medium to large effect for the treatment of AVH with rTMS. However, all studies so far investigated the effects of rTMS in treatment resistant schizophrenia patients as an ad-on or second-line treatment.

However, there are no studies to date that explored the effects of rTMS either as a first-line treatment or in the initial stage of the illness. This is surprising, considering the fact that rTMS is a safe treatment with minimal side-effects (Rossi, Hallett, Rossini, & Pascual-Leone, 2009) that could be used already in the earlier phase of treatment. Furthermore, another advantage of rTMS are the minimal side-effects associated with this treatment (Rossi et al., 2009). This stands in considerable contrast to the range of side-effects associated with antipsychotics (Leucht et al., 2017) that can be disabling leading to suffering for patients and lower quality of life. Therefore, it is crucial to develop new treatment options that in the future might provide alternatives to conventional therapy.

Noteworthy, previous studies in medicated patients focused mainly on treatment-resistant patients, which might be a special subgroup and not necessarily reflect the whole spectrum of schizophrenia patients including first episode patients who never had antipsychotic treatment. Therefore, investigating rTMS effects in patients from the whole schizophrenia spectrum are needed.

Further, the majority of studies used the standard protocol as described above that lasts for 10 consecutive days with one TMS session per day. Yet, daily administration of rTMS over the course of several days without antipsychotic medication could comprise risks, especially for patients suffering from additional psychotic symptoms. This may be one of the reasons that no study to date has investigated rTMS in patients with schizophrenia that did not take any antipsychotic medication.

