However, most of the studies included patients with medication-resistant AVH. No study to date investigated rTMS in medication-naïve, high-risk individuals for psychosis or patients who are currently not taking antipsychotics who suffer from AVH in the relative absence of other severe positive or negative symptoms (C. W. Slotema et al., 2014). This is surprising, considering the fact that rTMS is a safe treatment with minimal side-effects (Rossi et al., 2009) that could be used already in the earlier phase of treatment. TMS could be applied as a first-line treatment for patients who primarily suffer from AVH, thus, exhaust other therapeutic options before turning to antipsychotics that are often associated with considerable side effects (Leucht et al., 2017) that impact on the patient's quality of life.

Furthermore, it is crucial to investigate the effects of brain stimulation independently of potentially influencing effects of antipsychotic medication. Teasing apart the effects of brain stimulation and antipsychotic drugs would allow a clearer assessment of the effects of brain stimulation and would help determine if brain stimulation techniques are useful as a first-line treatment or better implemented as an add-on to the conventional drug therapy. Yet, daily administration of rTMS over the course of several days without antipsychotic medication could comprise risks especially for patients suffering from further psychotic symptoms. Therefore, reducing the time of rTMS administration would, on the one hand, diminishes this risk and, on the other hand, reveals potentially beneficial effects of rTMS on AVH within a day, rather than two or more weeks typically needed with the classical rTMS protocol. Yet, no study to date has investigated rTMS for AVH in patients with schizophrenia who do not take antipsychotic medication. We aim to bridge this gap.

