5 STUDY POPULATION

5.1 INCLUSION CRITERIA

In order to be eligible to participate in this study, an individual must meet all of the following criteria:

1. Provision of signed and dated informed consent form
2. Stated willingness to comply with all study procedures and availability for the duration of the study
3. Male or female, aged 18 to 65
4. Diagnosed with DSM V diagnosis of schizophrenia (295.90), schizoaffective disorder (295.70), or brief psychotic disorder (298.80), prone to AVH in the acute phases of the disorder

5. Willing to adhere to the rTMS regimen
6. Subtherapeutic antipsychotic serum level upon admission as per Nathan Kline Institute reference guidelines on antipsychotic therapeutic serum levels.
7. Agreement to adhere to Lifestyle Considerations (see section 5.3) throughout study duration

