5.2 EXCLUSION CRITERIA

An individual who meets any of the following criteria will be excluded from participation in this study:

1. Therapeutic level of antipsychotic medication
2. ECT or rTMS within three months (see the TMS screening questionnaire)
3. History of seizures
4. Presence of implanted electronic device or metal implant in the head and neck region (DBS, cochlear implant, etc.)
5. Pregnancy, as assessed with a pregnancy test prior to every MRI measurement, or lactation
6. Any active general medical condition or CNS disease which can affect cognition or response to treatment
7. Treatment with another investigational drug or other intervention within 2 weeks
8. Current diagnosis of delirium, dementia, or amnestic amnesiac disorder; Diagnosis of mental retardation; Current (within the past three months) diagnosis of active substance dependence, or active substance abuse within the past week as indicated by self-report.
9. Patients who are cognitively impaired and are thus not able to give informed consent

Note, that other medication such as antidepressant, pain killers, or sleep medication are no exclusion criteria per se. Yet, if these medications are needed for the treatment of other mental illnesses such as subsumed under point 5 or 7 of the exclusion criteria then patients cannot be included in the study.

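### Suicidal or homicidal risk is a listed reason to withdraw a participant, but the entry criteria do not address it before randomisation

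*Combined protocol and SAP*

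**What the plan says.** **Stop side.** Under AVH symptomatology, Section 2.2.1 covers worsening psychotic symptoms and, as the worst case, a patient who "gets suicidal or homicidal within the three days of the study, participation is terminated". Section 7.2 opens its list with "An investigator may discontinue or withdraw a participant from the study for the following reasons" and includes "Significant risk of suicidal or homicidal behavior (including aggressive behavior towards staff, others or themselves".

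**Entry side.** Section 5.1 begins "In order to be eligible to participate in this study, an individual must meet all of the following criteria" and gives seven items. Section 5.2 begins "An individual who meets any of the following criteria will be excluded from participation in this study" and gives nine. The synopsis (1.1) has its own shorter list and restricts entry to inpatients with current voices in an acute phase. None of the three lists mentions suicidal or homicidal risk, aggression or commanding voices. The nearest general item in 5.2 is "Any active general medical condition or CNS disease which can affect cognition or response to treatment", which does not name this risk.

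**Timing.** The schedule of activities (1.3) marks randomisation in the screening column and lists no assessment of suicide or violence risk. The schema (1.2) places the clinical interview at Visit 2.

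**After withdrawal.** Sections 6.4 and 9.3 analyse only patients who complete everything. Section 8.1 applies last observation carried forward to drop-outs and premature exits. Section 7.2 says that treated patients who are withdrawn will be replaced and that randomised but untreated patients may be.

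**The concern.** The plan treats this condition as a reason not to continue, but does not ask about it at the point where it decides who starts. The population makes the question a practical one. These are acutely psychotic inpatients who are not taking antipsychotics, and 2.2.1 opens its risk section with voices that may command or threaten harm.

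Two things are at stake. The first is safety: a patient whom the plan would allow to be withdrawn on this ground can be entered and allocated, possibly to sham, when the fact could have been established beforehand. The second is the integrity of the randomised set. A condition that existed before allocation surfaces only afterwards, so what could have been a screen failure becomes a withdrawal, with the missing data and replacement that follow.

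**Working it through.** The plan has no figure on this point, so the check sets the sections side by side.

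1. **Does a stop condition cover a risk already present at entry?** Section 2.2.1 does not: its verb describes a change during the study, and it is paired with worsening symptoms. Section 7.2 does: its item describes a state and sets no onset requirement.

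2. **How binding is each?** Section 2.2.1 is mandatory. Section 7.2 is discretionary. The two therefore differ in both trigger and force.

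3. **Does any entry criterion catch the same state?** All seven items in 5.1, all nine in 5.2 and the synopsis list were read. None does.

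4. **Does the plan align comparable conditions?** Yes. Pregnancy is exclusion item 5 in 5.2 and also a withdrawal reason in 7.2. Head and neck implants are exclusion item 4, and 7.2 has the matching MR contraindication. Suicidal or homicidal risk appears on the stop side only.

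5. **Does anything in the schedule catch it before allocation?** Section 1.3 lists nothing. Section 2.2.1 has the BAVQ-R given at every visit, and Section 3 ties that instrument to dangerousness only as monitoring for an increase. No entry threshold is set.

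6. **What happens to such a patient?** Section 5.4 defines a screen failure as someone who consents but is not then randomised. With randomisation at screening and no check before it, the patient can no longer be a screen failure. If withdrawn, the route is:
   - Analysis set: out under 6.4 and 9.3.
   - Conflicting rule: if rTMS stops before the fourth session, 8.1 carries the last observation forward. Section 3 fixes the baseline HCS at 10, so a patient with only a baseline score would enter as unchanged.
   - Replacement: promised in 7.2 if treated, optional if not.

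7. **Size.** The documents give no rate. One such patient is 1/40 = 2.5% of the planned sample, or 1/20 = 5% of an arm.

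**The case against.** The best defence is that silence in the entry lists is not the same as no safeguard. Section 5.5 has eligibility confirmed by trained raters after consent, and its compensation table shows clinical assessment at the screening visit. Section 4.1 offers treatment only where it is clinically indicated and benefit exceeds risk. Patients are inpatients, study staff stay in contact with the ward and the treating physician, and antipsychotics can be given at any time. The case report forms and manual of procedures are not among the documents and may contain more. All of this stands, and clinical judgement may well keep some such patients out. But none of it is an entry criterion on this risk. The physician's check in 5.5 concerns capacity to consent, and the ward safeguards act after entry.

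A reader might also infer several stronger points that the documents do not support:

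- **That 2.2.1 requires termination of anyone already at risk on entry.** It covers onset or worsening during the study. Pre-existing risk rests on 7.2 alone, where withdrawal is possible but not certain.
- **That randomisation takes patients off antipsychotics.** Patients are unmedicated or decline medication before allocation, and 5.3 says they are not asked to abstain.
- **That the rationale in 2.1 already implies a missing exclusion.** The statement that "daily administration of rTMS over the course of several days without antipsychotic medication could comprise risks, especially for patients suffering from additional psychotic symptoms" concerns multi-day treatment, and the plan's answer is the one-day schedule. The remark that "TMS could be applied as a first-line treatment for patients who primarily suffer from AVH" describes possible use; elsewhere 2.1 calls for patients from the whole spectrum.
- **That the comparison of arms is biased.** A condition present before allocation is independent of arm. Withdrawal for that reason alone narrows the population, and the documents show no mechanism that differs by arm.
- **That power falls.** If 5% to 15% of 40 (2 to 6 patients) were lost, two-sided t-test power at an effect size of 0.9 would go from 79.2% with 20 per arm to 77.0% with 19 or 72.1% with 17. But the rate is pure assumption, and the calculation needs every such patient to be withdrawn and none replaced. Section 7.2 promises replacement of treated patients and allows it for untreated ones.

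**Conclusion.** The gap is real and limited. As written, a patient who already meets the 7.2 condition is eligible, can be randomised while not taking antipsychotics, and may then be withdrawn. It is a mismatch between an entry list that is silent and a withdrawal list that is not. A second mismatch lies between a mandatory rule in 2.2.1 and a discretionary one in 7.2.

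The consequences are for patient safety and for avoidable exclusion after allocation, made harder to handle by the conflict between 6.4 and 9.3 on one side and 8.1 on the other. The frequency is unknown, so no total effect on the trial can be given. The conclusion assumes that no document outside the protocol adds an entry check, and that the 7.2 item means what it says in not requiring new onset.

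**What to change.** Reconcile 5.1 and 5.2 with 2.2.1 and 7.2, so that entry and stopping refer to the same condition in the same terms, and resolve whether ending participation is mandatory or discretionary. In 1.3, add a recorded check before randomisation of whether the plan's own stop condition is already present. A patient in whom it is present is then reported as a screen failure under 5.4 instead of a withdrawal after allocation. The clinical wording, the threshold and the method of assessment are for the sponsor's clinicians; this review proposes none.

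The cost is one aligned line in the entry criteria, one item on the screening case report form, and slightly fewer eligible patients. The conflict between the completer rule (6.4, 9.3) and carrying the last observation forward (8.1) needs its own correction, because patients whose risk arises after allocation will still be withdrawn.
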